5.4 Observation period

The observation period for this study will be set until Week 24 after the start of administration (cases treated with the drug for more than 25 weeks will be included in the separately planned Special Investigation on long-term use and observed for up to 96 weeks after the start of administration)

[figure not shown]
Clinical evaluation of tumor: Weeks 8, 16, and 24. For discontinued cases, if the clinical evaluation of tumor is not performed within 4 weeks prior to discontinuation, clinical evaluation of tumor will be performed at the time of discontinuation.

Adverse events: Until Week 24 after the start of administration. If the drug is discontinued before Week 24, observe until Day 28 after the discontinuation of administration.

This study will be conducted using a case report form divided into separate booklets. The results during the following observation periods will be recorded in the different booklets of the case report form.

| Booklet | Observation period |
|------------|---|
| Booklet 01 | Start of administration to Week 4 (Day 28) |
| Booklet 02 | Week 5 (Day 29) to Week 12 (Day 84) after start of administration |
| Booklet 03 | Week 13 (Day 85) to Week 24 (Day 168) after start of administration |

(Start of administration)
(Day 1)

Observation period and evaluation time points for each booklet of case report form

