## **5.2. Efficacy Analysis Set**

The efficacy analysis set basically consists of evaluable patients (patients considered to have undergone an appropriate evaluation).

However, patients who violate efficacy criteria among separately specified patient inclusion criteria will be excluded.

Not meeting conditions for target patients, experience of treatment with this drug, efficacy evaluation “unassessable” (not meeting conditions for assessment).

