## 6.2. Efficacy Endpoints

1. Response rate (percentage of complete response [CR] + partial response [PR])
2. Clinical benefit rate (percentage of CR + PR + stable disease [SD] for at least 24 weeks)
3. Progression-free survival (PFS): Time from the date of initiation of treatment with this drug in this study to the date progressive disease (PD) or all-causality death is first confirmed during the treatment period (including 28 days after the completion of treatment with this drug) and the period up to the date of final evaluation of tumor response. PD or death occurring during the treatment period (including 28 days after the completion of treatment with this drug) or the period up to the date of final evaluation of tumor response, whichever period is the earlier, will be handled as a PFS event, and patients without a PFS event will be censored at the date of final evaluation of tumor response. Patients with no record on tumor response at all will be censored at the date of initiation of treatment with this drug.

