#### **8.1.4. Analysis of Time Data (time to the onset of event)**

Ninety-five percent confidence intervals for median, first quartile, and third quartile by the Kaplan-Meier method will be calculated. In addition, Kaplan-Meier plots will be prepared.

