### 8.2.7. Efficacy Analysis

- **Response rate and clinical benefit rate**

The number and percentage of patients by best overall response, the response rate and its 95% confidence interval, and the clinical benefit rate and its 95% confidence interval will be tabulated in the safety analysis set and efficacy analysis set.

The response rate is defined as the percentage of patients whose best overall response is CR or PR.

The clinical benefit rate is defined as the percentage of patients whose best overall response is CR, PR, or SD.

The best overall response is defined as the best response among recorded overall response.

Table 1 of “New Guideline for the Assessment of Treatment Effect on Solid Cancer (Response Evaluation Criteria in Solid Tumors [RECIST] Guideline)–Japan Clinical Oncology Group [JCOG] version in Japanese” will be used for overall response, but overall response based on combinations of tumor response not corresponding to the table because of unknown data and no entry of data was uniquely defined. Therefore, the

tabulation analysis is not in complete compliance with the guideline and uses the guideline for reference.

**Table 1. Overall Response Based on Combinations of Tumor Response in Target and Non-target Lesions Including the Presence or Absence of New Lesions**

Target lesion	Non-target lesion	New lesion	Overall response
HCR	CR	Absent	CR
CR	IR/SD	Absent	PR
PR	Other than PD	Absent	PR
SD	Other than PD	Absent	SD
PD	Any response	Any response	PD
Any response	PD	Any response	PD
Any response	Any response	Present	PD

The following tumor response will be converted as shown by the arrow.

Non-target lesion: Absent → CR, not entered → IR/SD.

New lesion: Not entered → absent.

Overall response not corresponding to any combination in Table 1 after the above conversion will be considered as “unassessable.”

In addition, tabulation will be performed in the same manner by category shown below.

For items using reference laboratory test values, results using corporate reference values will be tabulated separately from results using institutional reference values as necessary.

- Site of metastasis [none, lung, liver, bone, lung + 1 organ, lung + 2 organs, lung +  $\geq 3$  organs,  $\geq 2$  organs other than lung, others];
- Whether criteria for proper use are met [yes, no];

- Prior treatment history [IFN- $\alpha$ , IL-2, Sutent, Nexavar, Afinitor, others];

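### The PFS censoring date in SAP 6.2 is not limited to evaluable tumor evaluations, so read literally an unassessable visit extends event-free follow-up and pushes the Kaplan-Meier curve upward

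*SAP*

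**What the plan says.** SAP 6.2 item 3 defines PFS from the start of treatment to the first PD or death. For everyone else it says "patients without a PFS event will be censored at the date of final evaluation of tumor response". The one exception is "Patients with no record on tumor response at all will be censored at the date of initiation of treatment with this drug".

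SAP 8.2.7 derives the overall response at each evaluation from Table 1, after filling some gaps: "Non-target lesion: Absent → CR, not entered → IR/SD" and "New lesion: Not entered → absent". It then adds: "Overall response not corresponding to any combination in Table 1 after the above conversion will be considered as" unassessable. There is no conversion for an absent or blank target lesion. SAP 6.2 does not mention unassessable evaluations, and SAP 7 (missing data) is marked as not applicable.

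Protocol 5.4 sets the schedule: "Clinical evaluation of tumor: Weeks 8, 16, and 24", plus an evaluation at discontinuation if none was done in the preceding 4 weeks. SAP 8.1.4 gives the planned output: "Ninety-five percent confidence intervals for median, first quartile, and third quartile by the Kaplan-Meier method will be calculated", with plots. SAP 5.2 excludes from the efficacy set patients with "experience of treatment with this drug, efficacy evaluation" unassessable.

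**The concern.** An unassessable visit is still a recorded visit, so the exception for patients without any record does not cover it. Take a patient with SD at Week 8 whose target lesions are not measured at Weeks 16 and 24. The last positive evidence of no progression is at Week 8, but the literal rule censors at Week 24, which is 24 − 8 = 16 weeks later.

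In a Kaplan-Meier estimate that patient stays in the denominator at Weeks 16 and 24 with no chance of a target-lesion PD being recorded. The estimated hazard at those visits falls and the curve rises. At the least, two programmers could derive different censoring dates from the same text, and the literal choice gives the more favourable curve. SAP 3 says that all planned analyses are performed for the re-examination application.

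**Working it through.** **No plan figure to reproduce.** The documents give no PFS rate, median or event count. The sample size rests on seeing at least one event of 1% incidence in 300 cases (1 − 0.99^300 = 0.951) and does not depend on PFS.

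**Which records become unassessable.** Going through Table 1 after the conversions leaves two kinds: (a) the target lesion is blank or not evaluable, with no non-target PD and no new lesion recorded; (b) target CR is paired with a non-target lesion that was not evaluated. Any recorded target PD, non-target PD or new lesion still gives PD.

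**Size, worked by life table.** Inputs:
- Visits at Weeks 8, 16 and 24 (Protocol 5.4).
- Assumed: exponential PFS with median 16 weeks; 20% of patients without recorded PD leave after each visit; each visit is unassessable with probability u = 0.10, at random; a PD missed at an unassessable visit is recorded at the next evaluable one.

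Probability of staying progression-free over 8 weeks: p = 2^(−8/16) = 0.7071, so 1 − p = 0.2929. True Week-24 PFS = 0.7071³ = 0.3536.

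*Literal rule (every attended visit counts):*
- Week 8: at risk 1; PD recorded 0.2929 × 0.9 = 0.2636; hazard 0.2636. Carried on: not progressed 0.7071 × 0.8 = 0.5657; missed PD 0.0293 × 0.8 = 0.0234.
- Week 16: at risk 0.5891; PD recorded (0.5657 × 0.2929 + 0.0234) × 0.9 = 0.1702; hazard 0.2889. Carried on: 0.5657 × 0.7071 × 0.8 = 0.3200, and (0.1657 + 0.0234) × 0.1 × 0.8 = 0.0151.
- Week 24: at risk 0.3351; PD recorded (0.3200 × 0.2929 + 0.0151) × 0.9 = 0.0980; hazard 0.2923.
- PFS = 0.7364 × 0.7111 × 0.7077 = 0.3706, which is **+1.7 points**.

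*Censoring at the last evaluable visit:* the risk set at each visit keeps only patients with an evaluable visit then or later. The factors are 0.9 at Week 24, 0.9 + 0.1 × 0.8 × 0.9 = 0.972 at Week 16, and 0.9 + 0.1 × 0.8 × 0.972 = 0.9778 at Week 8.
- At risk: 0.9778, 0.5726, 0.3016. Hazards: 0.2696, 0.2972, 0.3248.
- PFS = 0.7304 × 0.7028 × 0.6752 = 0.3466, which is **−0.7 points**.

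The same formulas with medians of 12, 16 and 24 weeks give these errors at Week 24, in points:

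| u | Literal rule | Last evaluable visit |
|---|---|---|
| 5% | +0.7 to +0.8 | −0.3 |
| 10% | +1.5 to +1.7 | −0.6 to −0.7 |
| 20% | +3.4 to +4.2 | −1.5 to −1.6 |

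**Second check.** A simulation of 600 patients added the discontinuation evaluation, with assumed PFS medians of 12, 20 or 30 weeks. Here only the final evaluation could be unassessable, in 5% to 30% of patients. The literal rule exceeded last-evaluable censoring at Week 24 by 0.7 to 0.9 points at 5%, 1.3 to 1.9 at 10%, 2.7 to 4.0 at 20% and 3.8 to 5.8 at 30%. The Kaplan-Meier median was the same under both rules in every scenario.

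**A simple remedy that fails.** Suppose that only visits with CR, PR or SD counted. Because 8.2.7 has no conversion for absent target lesions, a patient with non-target disease only would be unassessable at every event-free visit and censored at time 0, while any PD would still count. Assume that 10% of patients are of this kind and that nothing else is unassessable (median 16 weeks, 20% leaving):
- Week 8: at risk 0.9 + 0.1 × (0.2929 + 0.1657 + 0.0937) = 0.9552; hazard 0.2929 / 0.9552 = 0.3066.
- Week 16: at risk 0.9 × 0.5657 + 0.1 × (0.1657 + 0.0937) = 0.5351; hazard 0.1657 / 0.5351 = 0.3097.
- Week 24: at risk 0.9 × 0.3200 + 0.1 × 0.0937 = 0.2974; hazard 0.3152.
- PFS = 0.6934 × 0.6903 × 0.6848 = 0.3278, which is **−2.6 points**. Here the literal rule would be unbiased.

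**The case against.** The strongest reply is that the SAP never says an unassessable visit sets the PFS date. The term belongs to the response-rate section, and 6.2 could be read as meaning the last evaluation that yielded a response. The amendment log also says that a PFS tabulation was added to 8.2.7. That text was not available for this review and may name the analysis set or deal with these visits. This stands: the defect is a rule that permits the problem, not one that prescribes it.

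The efficacy-set exclusion in SAP 5.2 may narrow the issue, but probably does not remove it. Best overall response is the best of the recorded responses, so one SD visit appears to make a patient assessable. The visible text does not say which set PFS uses.

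The plan also reports quartiles and plots, not a Week-24 rate, and the median did not move in the simulation. That limits the practical effect, though the plotted curve would still be shifted.

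A reader might infer that PFS in this study is overstated, or that the extra follow-up was verified by nobody. The documents support neither. The first depends on the literal reading and on an unknown unassessable rate. The second fails where non-target and new lesions were actually reviewed, because a recorded PD there counts. It is fair only where those fields were blank and converted to no progression. A reader might also fear a bias of 6 to 7.5 points. That needs scans to be unassessable in 30% of progressed against 5% of unprogressed patients, and nothing in the documents points to such a pattern.

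**Conclusion.** The point holds as a gap in the PFS definition with a predictable direction. If unassessable visits count as the final evaluation, the Kaplan-Meier PFS curve is pushed upward. Under the stated assumptions the size at Week 24 is about 1 point at 5% unassessable, 1.5 to 2 points at 10% and 3.5 to 4 points at 20%.

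These figures rest on assumed exponential PFS, assumed drop-out, visits unassessable at random, and the three scheduled visits to Week 24. They are not estimates for this study, and the effect could be negligible if few visits are unassessable. PFS is one of three efficacy endpoints, was added in SAP version 3.0, and is descriptive in a study that SAP 4 calls non-confirmatory. The change is still worth making, because it is cheap and removes a choice that would otherwise be left to the programmer.

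**What to change.** In SAP 6.2 item 3, replace the censoring rule with the following. Patients without a PFS event are censored at the date of the last evaluable tumor evaluation showing no PD. An evaluation is evaluable if its overall response is CR, PR or SD. In patients without target lesions at baseline, it is evaluable if non-target and new lesions were actually assessed, not filled in by the blank conversions of 8.2.7, and showed no PD. Patients with no such evaluation and no PFS event are censored at the date of treatment initiation.

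The cost is a few sentences in the SAP and two conditions in the derivation program, which must keep the entries as they stood before conversion and flag patients without baseline target lesions. Follow-up becomes slightly shorter and PFS slightly less favourable. If visits are unassessable at random, a small downward bias remains, about 0.5 to 1.5 points at 10 to 20% unassessable. The second condition is needed to avoid the 2 to 3 point understatement that a plain CR/PR/SD rule would cause if 10% of patients had no target lesion.

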## 7. HANDLING OF MISSING DATA

Not applicable.

## **8. STATISTICAL METHODS AND ANALYSES**

### **8.1. Statistical Methods**

#### **8.1.1. Analysis of Continuous Data**

Summary statistics (number of patients, mean, standard deviation, median, maximum, and minimum) will be calculated.

#### **8.1.2. Analysis of Categorical Data**

The frequency of each category and its percentage will be calculated.

#### **8.1.3. Analysis of Binary Data**

Frequency and its percentage will be calculated. If the confidence interval for percentage is calculated, the 2-sided 95% confidence interval (exact method) will be calculated.

If a test is performed, Fisher's exact test will be performed for the relationship with nominal scale data and Cochran-Armitage test (exact method) for the relationship with ordered scale data.

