1 OBJECTIVES

The objective of this study is to assess the following subject matters in patients treated with TORISEL 25 mg Injection (hereinafter called this drug) in post-marketing actual use conditions, thereby providing proper-use information.

- (1) To confirm the effectiveness and safety of this drug under actual use conditions
- (2) To examine the onset state of adverse events and potentially influencing factors (particularly, major investigation items)
- (3) To examine the onset state and potential onset risk factors of interstitial lung disease

[Conditions for approval]

A drug use investigation must be conducted with all the patients treated with this drug until the data from a specified number of cases are accumulated after the marketing of this drug in order to understand the background information on patients treated with this drug, collect the data on the safety and effectiveness of this drug as early as possible, and take necessary measures to ensure the proper-use of this drug.

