## **4. HYPOTHESIS AND DECISION RULES**

Because this study is not a confirmatory study, tests are **CCI**. Unless otherwise specified, tests are 2-sided and the significance level is 5%. Two-sided confidence interval will be used in interval estimation, and the confidence coefficient is 95%.

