# **6. ENDPOINTS AND COVARIATES**

## **6.1. Safety Endpoints**

1. *Onset state of adverse events/adverse reactions (particularly the major investigation items).*
2. *Onset state of adverse reactions and potential influencing factors (particularly the major investigation items).*
3. *Safety in patients with special background (pediatric patients, elderly patients, pregnant women, patients with renal or hepatic dysfunction).*
4. *Safety in patients with hepatic dysfunction (including the comparative examination with results from the foreign phase 1 clinical study).*
5. *Onset state of interstitial lung disease (including asymptomatic cases with imaging findings of the disease).*

6. *Potential risk factors of interstitial lung disease.*
7. *Characteristics of interstitial lung disease (imaging findings, onset timing, duration, and breakdown by severity).*
8. *List of clinical course of interstitial lung disease (contents of treatment, response to treatment, and outcome) and clinical course after the drug is restarted (presence/absence of recurrence/exacerbation, etc.).*
9. *Onset state of various related events suspected of causing interstitial lung disease (pneumonitis/lung infiltration and pulmonary fibrosis, etc.).*
10. Duration of treatment (Defined as the period from the date of initiation of treatment with this drug to the date of completion of treatment with this drug in this study. Patients for whom the completion of treatment is not reported in this study will be censored at the date of last dose.).

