The number of patients with CTCAE Grade  $\geq 3$  adverse reactions and the incidence of CTCAE Grade  $\geq 3$  adverse reactions will be tabulated by SOC and PT by category shown below. •Further tabulation of serious adverse reactions” will be followed for categories.

- Seriousness;
- Known/unknown;
- Outcome;
- Timing of initial onset;
- Intervention;
- Administration of this drug;
- Duration of treatment;
- Total dose.

- **Further tabulation of adverse events**

The number of patients with adverse events and the incidence of adverse events will be tabulated by SOC and PT by category shown below. “• Further tabulation of serious adverse reactions” will be followed for categories.

- CTCAE Grade.

- **Further tabulation of unknown adverse reactions**

The number of patients with unknown adverse reactions and the incidence of unknown adverse reactions will be tabulated by SOC and PT by category shown below. “•Further tabulation of serious adverse reactions” will be followed for categories.

- Outcome.

- **Cumulative incidence of adverse reactions**

The cumulative incidence of adverse reactions will be graphically presented with the time to onset on the horizontal axis.

The cumulative incidence will be graphically presented in the same manner for interstitial lung disease, diabetes mellitus/hyperglycemia, hypercholesterolemia/hyperlipidemia, infection, mucositis-related adverse events, and skin disorder among major investigation items.

- **Cumulative incidence of CTCAE Grade  $\geq 3$  adverse reactions**

The cumulative incidence of CTCAE Grade  $\geq 3$  adverse reactions will be graphically presented with the time to onset on the horizontal axis.

The cumulative incidence will be graphically presented in the same manner for interstitial lung disease, diabetes mellitus/hyperglycemia, hypercholesterolemia/hyperlipidemia, infection, mucositis-related adverse events, and skin disorder among major investigation items.

- **Incidence of adverse reactions by patient demographic**

The number of patients with adverse reactions and the incidence of adverse reactions will be tabulated by item listed in “[Section 10.1.1. Patient demographics to be used to evaluate safety and efficacy.](#)”

Fisher’s exact test will be performed for nominal scale data and Cochran-Armitage test (exact method) for ordered scale data.

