Tabulation will be performed in the same manner for interstitial lung disease, diabetes mellitus/hyperglycemia, hypercholesterolemia/hyperlipidemia, infection, mucositis-related adverse events, and skin disorder among major investigation items.

For items using reference laboratory test values, results using corporate reference values will be tabulated in addition to results using institutional reference values.

- **Incidence of CTCAE Grade  $\geq 3$  adverse reactions by patient demographic**

The number of patients with CTCAE Grade  $\geq 3$  adverse reactions and the incidence of CTCAE Grade  $\geq 3$  adverse reactions will be tabulated by item listed in “[Section 10.1.1. Patient demographics to be used to evaluate safety and efficacy.](#)”

Tabulation will be performed in the same manner for interstitial lung disease, diabetes mellitus/hyperglycemia, hypercholesterolemia/hyperlipidemia, infection, mucositis-related adverse events, and skin disorder among major investigation items.

For items using reference values, results using corporate reference values will be tabulated in addition to results using institutional reference values.

- **Incidence of adverse reactions by medical history, prior treatment history, and concomitant therapy**

The number of patients with adverse reactions and the incidence of adverse reactions will be tabulated by category shown below.

The number of patients and incidence will be tabulated in the same manner for interstitial lung disease among major investigation items.

- Past medical history;
- Complications;
- Prior medications.

- **Incidence of CTCAE Grade  $\geq 3$  adverse reactions by medical history, prior treatment history, and concomitant therapy**

The number of patients with CTCAE Grade  $\geq 3$  adverse reactions and the incidence of CTCAE Grade  $\geq 3$  adverse reactions will be tabulated by category shown below.

- Past medical history;
- Complications;

- Concomitant medications;
- Non-drug therapies;
- Prior medications.
- **Subgroups**

Safety in the following subgroups will be analyzed.

1. Children (<15 years), adults ( $\geq 15$  years).
2. Elderly ( $\geq 65$  years), non-elderly (<65 years).
3. Presence or absence of pregnancy.
4. Presence or absence of hepatic dysfunction.
5. Presence or absence of renal dysfunction.
6. By indication.
7. By whether criteria for proper use are met.
8. History of hepatitis B, tuberculosis, and herpes zoster.
9. Severity of hepatic dysfunction.
10. Sex.

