**Nominal scale**

Item	Category	Remarks
AST/ALT $\leq$ 3-fold of institutional upper reference limit ( $\leq$ 5-fold of institutional upper reference limit if liver metastasis is observed)	Yes, No	
Chest CT normal	Yes, No	
Chest X-ray normal	Yes, No	
Measurement of markers for interstitial lung disease, such as KL-6, normal	Yes, No	
Pulmonary function test (PFT) normal	Yes, No	
Measurement of oxygen saturation normal	Yes, No	
Total cholesterol $\leq$ 350 mg/dL (9.9 mmol/L)	Yes, No	
Triglyceride $\leq$ 400 mg/dL (4.56 mmol/L)	Yes, No	
Hemoglobin A1C $<$ 10%	Yes, No	
Fasting blood glucose $\leq$ 1.5-fold of institutional upper reference limit	Yes, No	
Concomitant therapy (drug therapy)	Absent, Present	
Concomitant therapy (non-drug therapy)	Absent, Present	
History of smoking	Absent, Present	
Family history of diabetes mellitus	Absent, Present	
History of pulmonary surgery	Absent, Present	

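### In the readable SAP, potential ILD risk factors are examined only one at a time, so overlapping factors such as smoking, lung disease and abnormal baseline CT cannot be separated

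*SAP*

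**What the plan says.** Protocol 1 lists as its third objective "To examine the onset state and potential onset risk factors of interstitial lung disease", and SAP 6.1 carries it forward as item 6, "Potential risk factors of interstitial lung disease". Protocol 7.2.1 leaves the method for the major investigation items to the SAP.

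SAP 8.1 is readable in full. It offers summary statistics, frequencies, exact confidence intervals, two exact tests, and intervals for quartiles that "by the Kaplan-Meier method will be calculated". The tests are set out in 8.1.3 for binary data: Fisher's "exact test will be performed for the relationship with nominal scale data and Cochran-Armitage test (exact method) for the relationship with ordered scale data".

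SAP 8.2.6, on incidence of adverse reactions by patient demographic, goes through the items of Section 10.1.1: Fisher's "exact test will be performed for nominal scale data and Cochran-Armitage test (exact method) for ordered scale data". It then turns to ILD and other major items: "Tabulation will be performed in the same manner for interstitial lung disease, diabetes mellitus/hyperglycemia". SAP 4 says the study is not confirmatory and adds: "Unless otherwise specified, tests are 2-sided and the significance level is 5" per cent.

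In Section 10.1.1, "History of smoking", past lung disease, comorbid lung disease, past ILD, comorbid ILD, normal chest CT and normal chest X-ray are separate items, each tested alone.

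**The concern.** Several listed items describe much the same underlying state. Besides those just named, there are ILD markers such as KL-6, pulmonary function, oxygen saturation, dust exposure, pulmonary surgery and previous high-concentration oxygen. A single-factor table shows whether ILD is more frequent among smokers. It cannot show whether smoking still matters once pre-existing lung disease is known.

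The results are meant to feed proper-use information. If smoking only marks lung disease, the crude table may still present it as a risk factor. This is confounding between factors, and it would remain even if every patient were followed for the same time.

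**Working it through.** **1. The plan's own figures.** These are not in dispute.
- ILD incidence: 14/82 = 17.1% (Protocol 3).
- At least 40 ILD cases with probability of at least 95%: the text does not state the n beside this figure. With n = 300 (the 12-week target) the exact binomial gives P(X ≥ 40) = 0.968, which reproduces it. With n = 600 the probability is essentially 1.
- Expected ILD cases: 0.171 × 300 = 51 and 0.171 × 600 = 103. The 103 assumes the full 17.1% applies to all 600, although the plan expects half to stop before 12 weeks.

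**2. Number of single-factor comparisons.** The nominal list in Section 10.1.1 has 80 items. Seven are marked as not tested, so 80 − 7 = 73 are.

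**3. What a crude comparison can show (assumed inputs).** Let 25% of patients have lung disease, with ILD risk ratio R = 2 to 3 for lung disease and none for smoking. Let smoking be 70–75% with lung disease and 40–45% without. Let a and b be the proportions with lung disease among smokers and non-smokers. The crude smoking risk ratio is [1 + (R − 1)a] / [1 + (R − 1)b].
- Weak end (70% vs 45%, R = 2): a = 0.175/(0.175 + 0.3375) = 0.3415; b = 0.075/(0.075 + 0.4125) = 0.1538; ratio = 1.3415/1.1538 = 1.16.
- Strong end (75% vs 40%, R = 3): a = 0.1875/(0.1875 + 0.30) = 0.3846; b = 0.0625/(0.0625 + 0.45) = 0.1220; ratio = 1.7692/1.2439 = 1.42.
- Simulated Fisher tests at n = 600 and 17.1% ILD call smoking significant at 5% in about 12% to 46% of studies. A repeat gave 11% to 48%, the same within simulation error.

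**4. A second set of assumptions.** Smoking 50% with no effect of its own; lung disease in 30–40% of smokers and 10% of non-smokers; odds ratio for lung disease 2 to 4; ILD 17.1%; 2,000 runs per setting.
- Crude odds ratio for smoking: 1.17 to 1.62.
- Fisher significant at 5%: 6% to 30% at n = 300; 11% to 59% at n = 600.
- Mantel-Haenszel test stratified by lung disease: about 4% to 6% throughout.
- Control with lung disease at 30% in both groups: crude odds ratio 1.00, Fisher significant in about 4% to 5%. The excess comes from the link between the factors.

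**5. Is an adjusted model affordable?** At an assumed 10 events per parameter: 40/10 = 4, 51/10 ≈ 5, 103/10 ≈ 10. A short model is feasible.

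**The case against.** The strongest objection is redaction. SAP 8.2.6 ends in a blacked-out block, and the amendment log says redacted tabulation analyses were moved into 8.2.6 and 8.2.7. Calling them tabulations proves little, since the log uses similar words for the progression-free survival analysis. SAP 8.1 does not say its list is closed. A reader might infer that the plan contains no adjusted ILD analysis at all. The documents do not support that; they show only that none is readable. There is still indirect evidence: 8.1 includes Kaplan-Meier methods that serve duration of treatment and progression-free survival, whose analyses are not in the readable text, yet it names no regression method.

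Second, the aim is to examine potential factors in a study declared non-confirmatory, and no readable rule turns p < 0.05 into a declared risk factor. Single-factor screening is a recognised choice for that purpose. This lowers the stakes and makes clear labelling part of the remedy, but it does not remove the confounding.

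Third, 8.2.6 does tabulate ILD by past or present lung disease and by abnormal baseline imaging. The categories within those splits are features of the event, such as seriousness, grade, onset time and duration. Smoking and other candidate factors are not adjusted for.

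Finally, every driver of the illustration is assumed, and at the weak end with 300 patients the false-positive rate (6%) is close to nominal. That stands.

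**Conclusion.** The point holds in a limited form. In the readable SAP an explicit objective is served only by crude, one-factor-at-a-time comparisons, and these cannot separate overlapping lung-related factors. A correlate could therefore pass into the proper-use information as a risk factor.

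The size is illustrative only. The range of 12% to 46% at n = 600 depends on assumed prevalences and effects, and other plausible inputs give anything from near 5% to 59%. It would be wrong to infer that the study will name a false risk factor, or that smoking has no effect on ILD. The documents give no data on either. This is a cheap improvement to an exploratory analysis, not a flaw that invalidates the plan.

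**What to change.** Unless the redacted part of SAP 8.2.6 already contains one, add one pre-specified exploratory multivariable model for ILD:

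- **Model:** preferably Cox regression for time to first ILD onset, since onset date is collected (Protocol 6.8). Censor at the end of each patient's observation, so that unequal follow-up is handled as well.
- **Covariates, baseline only, in this order:** age, smoking, past or present lung disease or ILD, and abnormal baseline chest CT. Then, if the ILD count allows at about 10 events per parameter (an assumed rule of thumb): sex, lung metastasis, pulmonary surgery or dust exposure, and prior drug therapy.
- **Few events:** if ILD cases are near the plan's 40, keep the first four, including baseline CT, or use a penalised fit.
- **Reporting:** give adjusted estimates with 95% confidence intervals beside the crude table, and label all single-factor results as unadjusted associations.

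The cost is one SAP paragraph and one model on data already collected. Patients with missing covariates drop out, and SAP 7 gives no missing-data rule, so report the number used. Estimates for strongly overlapping factors, such as lung disease and abnormal CT, will be imprecise and should be presented as such.
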